8.2.5.2 Quality of Life Questionnaire for Bone Metastasis (QLQ-BM22)

~~To assess specific disease sites, symptoms and/or treatment related quality of life issues related to bone metastasis; the QLQ C30 will be supplemented with QLQ BM22 (Chow et al. 2009). QLQ BM22 contains 22 items, conceptualized into both symptom scales (five painful sites and three pain characteristics) and functional scales (eight functional interference and six psychosocial aspects).~~

8.3. INFORMATION ON GENERAL HEALTH STATUS

In addition to records of observations made at specific times, ~~unexpected signs and pain associated symptoms~~ related to analgesic treatment will be recorded in the clinical study records throughout the study.

The following parameters will be collected during this study at specific timepoints as described in the Study Schedule (Sections 16.1 and 16.2):

- ~~Pain associated S~~symptoms related to pain treatment (e.g. nausea).
- Potential historical laboratory analysis data (biochemistry and hematology data) defined as the most recent safety laboratory analysis obtained within one month before the screening and/or ongoing laboratory safety analysis and urine analysis, if available, performed as part of patient management by the Investigator. In case several safety laboratory analysis are performed during the study, only one per week will be recorded.
- ~~Physical examination (at screening visit) and a~~Abbreviate physical examination (at Visit 4 or early discontinuation visit) screening Visit and Visit 2.
- Body weight (at screening)

8.3.1 SYMPTOMS MONITORING

Symptoms Collection and Reporting

At ~~visite~~enrolment, study site personnel will record the occurrence, time of onset, nature and severity of ~~each patient pre-existing conditions and~~ symptoms related to ~~pain~~analgesic treatment. ~~After the ICD is signed, Up to Visit 24, site personnel will record any change in the occurrence and nature of symptoms related to pain condition~~ analgesic treatment or having an impact on pain evaluation. The nature, time of onset, duration, severity will be documented and each symptom will be classified by the most suitable term from a version of a Medical Dictionary for Regulatory Activities (MedDRA) agreed by the Sponsor and other parties involved in the study.

The condition of each patient will be monitored throughout the study. In addition, any sign or symptom related to pain treatment will be observed and elicited at least at each visit by open questioning, such as “How have you been feeling since you were last asked?”

8.3.2. SERIOUS ADVERSE EVENT AND REPORTING

~~Not applicable. As this is an (observational study) all serious symptoms that will occur during the observational period will only be reported in the final study report. Nevertheless, if a patient is withdrawn from the study because of an SAE, this information will be collected.~~

8.4. STUDY PROCEDURE PRIORITY ORDER

Figures ~~2, 3 and 4~~ to 5 in Section 4.1 are describing the sequence of procedures at each visit.

8.5.2. COMPLIANCE TO TIMING OF PROCEDURES

The Investigator should make a reasonable attempt to complete the scheduled study procedures on the appropriate scheduled visit and in the appropriate sequence.

The specifications in this protocol for the sequence of procedures are given as targets, to be achieved ~~within reasonable limits~~ if possible.

It is recognized, ~~however,~~ that deviations may occur for logistic or other reasons and will not be considered as protocol violations. The scheduled timepoints may be subject to ~~minor~~ alterations; however, the actual time must always be correctly recorded in the CRF, diary or other documents.

8.5.3. COMPLIANCE TO ANALGESIC PATIENT 'S THERAPY

Patient's compliance ~~with~~ to prescribed analgesic medication will be assessed at each visit by direct questioning and checking diary. The investigator will evaluate if patient fails to take more than 50% of the prescribed analgesic medication for the visit interval.

~~A patient will be considered as non-compliant if he/she fails to take the prescribed analgesic medication for more than 50% of the prescribed dose in a visit interval. A patient will be considered significantly non-compliant if he/she is judged by the Investigator to have repeatedly (for 2 visit intervals) taken less than 50 % of the prescribed amount of medication. As a result, significantly non-compliant patients may be discontinued from the study.~~

8.5.4. COMPLIANCE TO STUDY VISITS

Depending on patient general health status, visits to the Investigator site ~~will~~ may occur ~~approximately every 2~~ after enrolment at interval of 2 or 4 weeks. ~~However, visits may~~ Visits schedule can be adapted according to Investigator-patients agreement, as presented in Tables 1 and 2.

Table 1 herebelow was removed:

Table 1. Study Visits with Allowed and Suggested Time Intervals

Visit Number	Time Interval (Days)	
	Suggested	Allowed
Visit 1	-7 to -14 days	-5 to -16 days
Visit 2	Day 1	Day 1
Visit 3	14 days	10 to 18 days
Visit 4	28 days	24 to 32 days
Phone Call	35 to 49 days	33 to 51 days

And replaced by:

Table 1. Study Visits with Allowed and Suggested Time Intervals – First Case Scenario – Enrolment at Visit 1

Visit Number	Time Interval (Days)	
	Suggested	Allowed
Visit 1 (Screening and Enrolment)	Day 1	
Intermediate Phone Call	Day 15	Day 13 to 17
Optional intermediate evaluation Visit	Day 15	Day 13 to 19
Visit 2	Day 29	Day 29 to 43
Phone Call	Visit 2 Day + 7 days	Visit 2 Day + 14 days

Table 2 herebelow was added:

Table 2. Study Visits if with Allowed and Suggested Time Intervals – Second Case Scenario – Enrolment at Visit 1A

Visit Number	Time Interval (Days)	
	Suggested	Allowed
Visit 1A (Screening and Enrolment)	Day 1	
Visit 1B	Day 8	8 to 29 days
Intermediate Phone Call	Visit 1B Day + 14 days	Visit 1B Day + 12 to 16 days
Optional intermediate evaluation Visit	Visit 1B Day + 14 days	Visit 1B Day + 12 to 18 days
Visit 2	Visit 1B Day + 28 days	Visit 1B day + 28 to 42 days
Phone Call	Visit 2 Day + 7 days	Visit 2 Day + 14 days

8.5.5. COMPLIANCE TO DIARY COMPLETION

Compliance to diary completion (APS, WPS, ~~current and~~ rescue analgesic treatment recording) will be checked by Investigator at each visit ~~Visits 2, 3, 4 and early discontinuation~~ at Investigator site.

10.1.1.1. Analysis Populations

A special set of features – the target features – characterize the analgesic efficacy and are defined as follows:

- APS difference with respect to baseline (primary endpoint)
- WPS difference with respect to baseline (secondary endpoints)
- BPI difference with respect to baseline (secondary endpoints)

- IGAC difference with respect to baseline (secondary endpoints)
- PGAC difference with respect to baseline (secondary endpoints)
- QLQ-C30 and ~~QLQ-BM22~~ with respect to baseline (secondary endpoints)
- CPAs difference with respect to baseline (secondary endpoints)

10.1.4. STUDY PARTICIPANT CHARACTERISTICS

The patient's age, sex, ~~weight~~ or other demographic characteristics will be recorded and may be used in the pharmacodynamic analyses as quantitative or classification variables.

10.1.5. STATISTICAL EVALUATION OF SYMPTOMS

All prescribed analgesic treatment, analgesic rescue medication and symptoms related to pain treatment will be listed, and if the frequency of symptoms allows, they will be summarized using descriptive procedure.

Section 16.1. Attachment 1 – Study Schedule on next page was removed :

Abbreviations:

APS = Average pain score; BPI = Brief Pain Inventory; DMA = dynamic mechanical allodynia; DN4= Douleur Neuropathique en 4 questions; IGAC=Investigator Global Assessment of Changes; MPT= mechanical pain threshold; NPSI= Neuropathic Pain Symptom Inventory; PA = painful area; PCS= Pain Catastrophizing Scale; PGAC= Patient Global Assessment of Changes; QLQ-C30=quality-of-life questionnaire in 30 questions; QLQ-BM22 = quality-of-life questionnaire in 22 questions in bone metastasis; SA= static allodynia; TPS= thermal pain sensitivity; WPS = Worst pain score.

- a Aliquot of standard safety laboratory blood sample for genotyping is optional in this study (will be performed if patient gives his consent by signing the genotyping informed consent document). The aliquot can be taken at any time between Visit 2 and 4
- b Abbreviated physical examination
- c Potential historical safety laboratory data (biochemistry, hematology) defined as the most recent safety laboratory data obtained within one month before screening visit and/or standard safety laboratory analysis and urinalysis performed during the study as part of regular patient management by Investigator will be collected
- d Multidimensional Health Locus of Control Scale (MHLCS), Hospital Anxiety and Depression Scale (HADS), Revised Life Orientation Test (LOT-R) and Expectation questionnaire.
- e Only QLQ-C30.
- f Compliance to prescribed analgesic treatment will be followed through diary completion and direct questioning.
- g The Clinical pain assessments will include the following measurements: PA, SA, DMA, MPT and TPS.
- h APS and WPS will be collected in the diary. APS and WPS at visit 1 will be completed at site by patient with Investigator site staff help, if needed. The last APS and WPS will be completed by patients during the phone call with the Investigator.

And replaced by Section 16.1. Attachment 1 – Study Schedule – Enrolment at Visit 1 on next page

Abbreviations:

APS = Average pain score; BPI = Brief Pain Inventory; DMA = dynamic mechanical allodynia; DN4= Douleur Neuropathique en 4 questions; HADS = Hospital Anxiety and Depression Scale; IGAC=Investigator Global Assessment of Changes; LOT-R = Revised Life Orientation Test; MHLCS = Multidimensional Health Locus of Control Scale; MPT= mechanical pain threshold; NPSI= Neuropathic Pain Symptom Inventory; MPA = Most Painful Area; PCS= Pain Catastrophizing Scale; PGAC= Patient Global Assessment of Changes; QLQ-C30=quality-of-life questionnaire in 30 questions; SA= static allodynia; TPS= thermal pain sensitivity; WPS = Worst pain score.

- ^a Aliquot of standard safety laboratory blood sample for genotyping is optional in this study (will be performed if patient gives his consent by signing the genotyping informed consent document). The aliquot can be taken at any time during the study.
- ^b Potential historical safety laboratory data (biochemistry, hematology) defined as the most recent safety laboratory data obtained within one month before screening visit and/or standard safety laboratory analysis and urinalysis performed during the study as part of regular patient management by Investigator will be collected (one per week if several during the study).
- ^c Compliance to prescribed analgesic treatment will be followed through diary completion and direct questioning.
- ^d The Clinical pain assessments will include the following measurements: MPA, SA, DMA, MPT and TPS.
- ^e APS and WPS will be collected in the diary. APS and WPS at visit 1 will be completed at site by patient with Investigator site staff help, if needed. The last APS and WPS will be completed by patients during the phone call with the Investigator. At Visit 1, the Weekly APS during the preceeding week will be assessed for enrolment.
- ^f Optional Intermediate Evaluation Visit will be organized within the next days after the intermediate phone call at the discretion of the Investigator.

SECTION 16.2. ATTACHMENT 2 – STUDY SCHEDULE – ENROLMENT AT VISIT 1A WAS ADDED

Visit	Screening Enrolment	Observational Period			Follow UP / Early Discontinuation Phone Call
	1A	1B	Optional Intermediate Evaluation ^f	2	
Days	Day 1	Day 8 (+21 days)	Visit 1B Day+ 14 days (+12 to +18 days)	Visit 1B Day + 28 days (+ 14 days)	7 days after Visit 2 (+ 7 days)
Informed Consent (general and genotyping) ^a	X				
Demographics	X				
Abbreviated physical examination	X			X	
Primary disease and Relevant Medical History	X				
Primary disease treatment history	X				
Analgesic history (within 1 month before enrolment)	X				
Pre-existing Conditions/Symptoms related to pain treatment	X	X	X	X	X
Cancer Concomitant Medications	X	X	X	X	X
Inclusion/Exclusion Criteria	X				
Enrolment into study	X				
Clinical Pain Assessments ^d	X		X	X	
DN4, NPSI	X				
Expectation questionnaire	X				
QLQ-C30	X			X	
BPI (short form)	X		X	X	
IGAC and PGAC	X			X	
APS and WPS ^e	X			X	X
Laboratory analysis ^b					
Aliquot of blood sample for genotyping purpose ^a					
Diary completion					
Compliance to diary completion		X	X	X	
Compliance to prescribed analgesic treatment ^c		X	X	X	

Analgasic treatment review	←—————→				
Questionnaires MHLCS, HADS, LOT-R, PCS		X			

Abbreviations:

APS = Average pain score; BPI = Brief Pain Inventory; DMA = dynamic mechanical allodynia; DN4= Douleur Neuropathique en 4 questions; HADS = Hospital Anxiety and Depression Scale; IGAC=Investigator Global Assessment of Changes; LOT-R = Revised Life Orientation Test; MHLCS = Multidimensional Health Locus of Control Scale; MPT= mechanical pain threshold; NPSI= Neuropathic Pain Symptom Inventory; MPA = Most Painful Area; PCS= Pain Catastrophizing Scale; PGAC= Patient Global Assessment of Changes; QLQ-C30=quality-of-life questionnaire in 30 questions; SA= static allodynia; TPS= thermal pain sensitivity; WPS = Worst pain score.

- a Aliquot of standard safety laboratory blood sample for genotyping is optional in this study (will be performed if patient gives his consent by signing the genotyping informed consent document). The aliquot can be taken at any time during the study.
- b Potential historical safety laboratory data (biochemistry, hematology) defined as the most recent safety laboratory data obtained within one month before screening visit and/or standard safety laboratory analysis and urinalysis performed during the study as part of regular patient management by Investigator will be collected (one per week if several during the study).
- c Compliance to prescribed analgesic treatment will be followed through diary completion and direct questioning.
- d The Clinical pain assessments will include the following measurements: MPA, SA, DMA, MPT and TPS.
- e APS and WPS will be collected in the diary. APS and WPS at visit 1A will be completed at site by patient with Investigator site staff help, if needed. The last APS and WPS will be completed by patients during the phone call with the Investigator. At Visit 1A, the Weekly APS during the preceeding week will be assessed for enrolment.
- f Optional Intermediate Evaluation Visit will be organized within the next days after the intermediate phone call at the discretion of the Investigator.

Abbreviations

ECOG	Eastern Cooperative Oncology Group
MPA	Most painful area
QLQ-BM22	Quality-of-life questionnaire for bone metastasis in 22 questions
WAPS	Weekly Average Pain Score

This statistical analysis plan covers the interim and final analyses of the Oncopain study T2001-01. As specified in the study protocol, the interim analysis will be executed as soon as 60 patients have completed the study.

The primary objective of the complete study consists in finding predictive factors of pain management and analgesic treatment efficacy in patients suffering from CIBP (cancer-induced bone pain). The analyses necessary to achieve this objective are very complex to conduct, due to the complexity of the data available. Secondary objectives describe intermediate milestones which will be reached during these analyses.

An interim analysis is also planned for the validation of sample size and necessary items among the personality tests.

All statistical analyses related to the study will be the responsibility of DNAlytics or designee. They will be conducted on the full analysis set. This set includes all data from patients who have been screened and who completed the study (no drop-outs). No safety analyses will be conducted during the interim study. The safety analyses on the complete database will be performed by the sponsor and reported in the Clinical Study Report. Additional exploratory analyses of the data will be conducted as deemed appropriate.

All hypothesis tests will be conducted at a two-sided alpha level of 0.05, unless otherwise stated.

Name	Company	Role
[name]	DNAlytics	Study design, analysis implementation, reporting
[name]	DNAlytics	Study design, analysis review, reporting
[name]	DNAlytics	Study design, analysis and report review
[name]	Tools4Patient	Study design. As study sponsor representative, monitors data analysis progress.

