4.2. RATIONALE FOR THE STUDY DESIGN

4.2.1. POPULATION SELECTION AND SAMPLE SIZE

It is intended that up to 180 patients with CIBP will be enrolled to ensure that up to approximately 140 patients complete the study.

No a priori hypothesis tests or precision confidence intervals were used to determine the sample size. This sample size is rather justified by similar studies described in literature.

In the field of CIBP, several works have been reported. For example, Langford studied 97 cancer patients with CIBP, and managed to model the pain evolution for a particular subgroup of patients (Langford et al. 2011). Scott showed a link between QST and analgesia response on 23 patients suffering from CIBP. In other domains that are close, other works have been reported as well (Scott et al. 2012). First, Attal managed to show the relation between a pain-related marker (thermal hyperalgesia) and oxalyplatin neurotoxicity in cancer patients, based on a cohort of 48 patients (Attal et al. 2009). Second, Geber showed the ability of some psychological traits to discriminate between patient subgroups with different pain evolution scenarios based on a cohort of 146 patients suffering from chemotherapy-induced neuropathy (Geber et al. 2013).

The considered sample size for this trial seems therefore reasonable: higher than the sizes of the samples cited above. This larger number is motivated by the more complete set of features studied in the current study (patient history, psychological traits, pain assessments). Moreover as presented in Section 4.2.3, an interim analysis will be performed to confirm the final sample size of the study.

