10. STATISTICAL ANALYSES

10.1. DATA ANALYSIS PLANS

10.1.1. GENERAL CONSIDERATIONS

For all enrolled patients, pharmacodynamic analyses will be conducted on the full analysis set.

All tests of treatment effects will be conducted at a two-sided alpha level of 0.05, unless otherwise stated.

Additional exploratory analyses of the data will be conducted as deemed appropriate.

Detailed plan for the statistical methods for the safety and other variables will be provided in a Statistical Analysis Plan (SAP). This plan will be finalized prior to database lock.

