10.1.1.1. Analysis Populations

Statistical analysis and data tabulation will be performed using the full patient population unless specified otherwise.

The patients constitute data vectors of potentially all data sources:

- CRF entries,
- Item-level entries from personality questionnaires
- Facet-level summaries from personality questionnaires
- Meta-level summaries from personality questionnaires
- Diary entries
- Meta-level summaries from diary
- Pain evaluations

At any time during the statistical analyses, a subset of those vector entries (thus reducing the population to some of these input features only) might be considered.

In some exploratory analyses, new populations might also be defined, for example based on sub-groups of patients showing similar pain evolution throughout the study.

A special set of features – the target features – characterize the analgesic efficacy and are defined as follows:

- APS difference with respect to baseline (primary endpoint)
- WPS difference with respect to baseline (secondary endpoints)
- BPI difference with respect to baseline (secondary endpoints)
- IGAC difference with respect to baseline (secondary endpoints)
- PGAC difference with respect to baseline (secondary endpoints)
- QLQ-C30 with respect to baseline (secondary endpoints)
- CPAs difference with respect to baseline (secondary endpoints)

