1.1 Responsibilities

1.2Changes from Protocol

- A secondary endpoint was added for the analgesic treatment efficacy: Patient's daily APS and the linear regression coefficient of its daily evolution
- Secondary objectives of the final study were precised, while they were absent from the protocol

1.3Amendment Rationale

The primary study objective is the prediction of individual analgesic treatment efficacy. All primary and secondary endpoints concerning treatment efficacy were based on differences between weekly average of pain measures at baseline and at the end of the follow-up period. Due to frequent changes in the analysis therapy of cancer patients with bone metastases, it is essential to have a temporal granularity finer than the 4 weeks (i.e. follow-up duration). Therefore an additional endpoint was added for describing the daily values of APS and its linear trend throughout follow-up.

No secondary objective was described in the study protocol. For the sake of clarity, the current analysis plan describes 3 secondary objectives, all of which can be considered as intermediary milestones necessary in order to reach the (unmodified) primary objective of the study.

2 Study objectives

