2.4 Primary Endpoint

Individual analgesic treatment efficacy endpoint: patient's change from baseline of pain severity, as measured by the weekly means of the daily Average Pain Scores (APS).

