2.5 Secondary Endpoints

- Individual analgesic treatment efficacy: Patient's daily APS and the linear regression coefficient of its daily evolution
- Individual analgesic treatment efficacy: Patient's change from baseline of
 - Pain severity, as measured by the weekly means of the daily Worst Pain Score (WPS),
 - Pain severity and interference as measured by the Brief Pain Inventory (BPI),
 - Investigator and Patient Global Assessment of Changes (IGAC and PGAC),
 - Pain intensity measured after Clinical Pain Assessments (CPAs) at Visit 2,
 - Quality-of-Life Questionnaire in 30 questions (QLQ-C30).
- Correlation between pain severity and clinical pain assessment as measured by:
 - Pain severity, as measured by the weekly Average Pain Score (APS) at Visit 1 and 2,
 - Pain intensity measured after Clinical Pain Assessments (CPAs) at Visit 1 and 2.

Variables used as predictive factors rather than as endpoints are described hereunder in Section 4.2.

3 Summary of Study Design

See the latest protocol version.

4 Populations for Analyses

Statistical analysis and data tabulation will be performed using the population of completers unless specified otherwise. This set includes all data from patients who have been screened, included and who completed the study (no drop-outs).

For the interim analysis, only patients who completed the study before the interim database transfer will be included.

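### The SAP gives the name full analysis set to completers only, where the protocol refers to all enrolled patients, and does not declare the change; on the planned figures about 40 of 180 (22%) are left out

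*SAP*

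**What the plan says.** Protocol 10.1.1 states: "For all enrolled patients, pharmacodynamic analyses will be conducted on the full analysis set". Protocol 10.1.1.1 sets the default: "Statistical analysis and data tabulation will be performed using the full patient population unless specified otherwise". Under protocol 5.1 a patient counts as enrolled once eligible and assessed with the CPAs at Visit 1 or 1A; completing the study is not required.

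The SAP introduction keeps the name but defines the set differently: "This set includes all data from patients who have been screened and who completed the study (no drop-outs". SAP section 4 follows the protocol's default sentence with another population in it: "Statistical analysis and data tabulation will be performed using the population of completers unless specified otherwise".

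SAP 1.2 declares two changes from protocol. One is the added endpoint on daily APS and its slope; the other reads "Secondary objectives of the final study were precised, while they were absent from the protocol". SAP 1.3 gives reasons for those two only.

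On numbers, protocol 4.2.1 plans that "up to 180 patients with CIBP will be enrolled to ensure that up to approximately 140 patients complete the study". Protocol 5.8.3 foresees no replacement.

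**The concern.** The same name covers two different populations, and the section meant to list departures is silent. A reader of the report who sees full analysis set would take it to mean everyone enrolled, when it means those who stayed to the end.

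The exclusion happens after enrolment, so it can depend on how the patient fared. If patients whose pain is rising leave more often, the APS trend among completers looks too favourable; if improving patients leave, the error runs the other way. The restriction also discards usable data: diaries run until early discontinuation (protocol 7.2.2.1), and an APS is scheduled at the early discontinuation call (protocol 16.2 and its footnote e).

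**Working it through.** **1. Planned loss.** The protocol states no drop-out rate and no derivation of 180 or 140, so there is no figure of the plan's own to reproduce. Directly: 180 − 140 = 40, and 40/180 = 22.2%. Reading approximately 140 as 130 to 150 (assumed) gives 50/180 = 27.8% to 30/180 = 16.7%. Both planning figures are upper limits, so 22% is not a ceiling: with 120 completers of 180 the loss would be 60/180 = 33.3%.

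**2. Which analyses need completion.**

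| Analysis | Data needed | Visit 2 or final week needed? |
|---|---|---|
| A1 | Baseline variables | No |
| A2.1 | Daily diary APS, one slope per patient | No |
| A3 (the SAP's primary-objective analysis) | Diary days with and without a treatment; baseline predictors | No |
| Primary endpoint, WPS change | "differences between weekly average of pain measures at baseline and at the end of the follow-up period" (SAP 1.3) | Yes |
| BPI, IGAC/PGAC, CPA, QLQ-C30 change | Visit 2 assessment | Yes |

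In the two-visit scenario MHLCS, HADS, LOT-R and PCS are completed only at Visit 1B, so a patient who leaves before it lacks those predictors under any definition of the set.

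**3. A2.1 if drop-out depends on trend.** Everything in this step is assumed, except the enrolment of 180, the implied 22.2% loss and the two-sided 0.05 level. True slopes are normal with mean zero and SD 0.02, 0.05 or 0.08 NRS points per day. The log-odds of drop-out are linear in the slope, with the stated odds ratio (OR) per SD for a rising slope. Daily residual SD is 1.2, independent between days. Completers have 29 diary days and drop-outs 5 to 21. Rejection rates of the Wilcoxon test, simulated, as ranges over the three slope SDs:

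| OR | Shift among completers (slope SDs) | Completers only | Drop-outs added, ≥5 entries | Drop-outs added, ≥14 entries |
|---|---|---|---|---|
| 1.5 | −0.086 | 9–17% | – | – |
| 2 | −0.144 | 16–37% | about 6–8% | about 10–12% |
| 3 | −0.204 | 29–66% | about 7–12% | about 14–23% |

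The last two columns assume that every drop-out's diary is returned. At OR 1 the completers-only rate, and the rate with drop-outs added at ≥5 entries, stay at about 4–6%.

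Size of the shift over the 21 days between the first and last week of a 4-week follow-up = shift in SDs × slope SD × 21:
- OR 2: 0.144 × 0.02 × 21 = 0.06 to 0.144 × 0.08 × 21 = 0.24 NRS points.
- OR 3: 0.204 × 0.02 × 21 = 0.09 to 0.204 × 0.08 × 21 = 0.34.

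**4. A2.3, the correlation of baseline features with slope.** The exclusion itself matters little: a true correlation of 0.30 becomes 0.296, 0.289 and 0.281 at OR 1.5, 2 and 3. Adding very short diaries can do more harm. The standard error of a slope from n daily entries is 1.2/√(n(n² − 1)/12):
- n = 5: 1.2/√10 = 0.38 per day
- n = 14: 1.2/√227.5 = 0.08
- n = 29: 1.2/√2030 = 0.027

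These compare with a true slope SD of 0.02–0.08. Power for a true correlation of 0.30 (Pearson, unadjusted 0.05, OR 1), completers only versus drop-outs added:

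| Slope SD | Minimum 5 entries | Minimum 14 entries |
|---|---|---|
| 0.02 | 57% to 21% | 58% to 51% |
| 0.05 | 87% to 61% | 88% to 89% |
| 0.08 | 93% to 84% | 94% to 96% |

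With Spearman the loss at a 5-entry minimum is smaller (54% to 41%, 86% to 82%, 89% to 91%). SAP 5.2.3 does not say which correlation it will use.

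The effect on A3 was not computed.

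**The case against.** The SAP states its population openly, twice. The protocol does not formally define the full analysis set, allows other populations where specified, and leaves detailed methods to the SAP. A reader might infer that the SAP breaches the protocol; the documents do not support that. The SAP may set another population. What stands is that it reverses the default under an unchanged name without listing it in 1.2.

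The harm is conditional. No passage links drop-out to pain trend, and all ORs and SDs above are assumed. A mean trend of exactly zero is also a weak benchmark: patients enter with a WAPS of at least 4, and analgesia is initiated or reviewed at enrolment, so some trend is plausible. The size of the shift then matters more than the rejection rate, and it is small on a 0–10 scale. This is fair. SAP 4.1 and protocol 10.1.3 also have discontinuations, their extent and known reasons reported, but that does not show whether the leavers' pain was rising or falling.

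The 22% is not all caused by the SAP's wording. Drop-outs without a usable diary or Visit 1B questionnaires leave A2 or A3 under any definition, so the recoverable number is smaller and unknown. The conflict also concerns mainly the final analysis, because protocol 4.2.3 itself triggers the interim on about 60 completers. Both points stand.

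**Conclusion.** The firm defect is a misnamed and undeclared post-enrolment exclusion, planned at about 40 of 180 patients, and it is unnecessary for A1, A2.1 and A3. It should be fixed before the final analysis.

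The possible bias is secondary and rests on assumption. If drop-out is related to trend, the A2.1 test (secondary objective 3) rejects a true zero mean trend in about 16–37% of trials at OR 2 and 29–66% at OR 3, for a shift of 0.06–0.34 NRS points over 21 days. If drop-out is unrelated to trend, there is no bias. A reader might infer that the primary objective is compromised. The documents do not show this: A3 was not evaluated, and A2.3 is little affected by the exclusion.

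**What to change.** - **Names.** Define the full analysis set as all enrolled patients. Rename the present set completers, keep it as a sensitivity analysis, and list any remaining departure in SAP 1.2.
- **A1.** All enrolled patients with the variable observed.
- **A2.1.** All enrolled patients with a pre-stated minimum number of diary APS entries.
- **A2.3.** Do not add very short unweighted slopes. Set a higher minimum (for example 14 entries) with Spearman correlation, or keep completers as the primary set there. A higher minimum removes less of the A2.1 bias, so A2.1 and A2.3 may use different minimums.
- **A3.** All enrolled patients who meet its day-level scope and have the baseline predictors. Report how many are lost for missing MHLCS, HADS, LOT-R or PCS.
- **Endpoints that need Visit 2 or a final diary week**, including the primary endpoint ("change from baseline of pain severity, as measured by the weekly means of the daily Average Pain Scores (APS"). Use enrolled patients with the endpoint observed and report the number missing. This does not remove possible bias there.
- **Two tables.** Completers versus drop-outs at baseline; and drop-outs' APS change from Visit 1 or 1A to the early discontinuation call, a direct look at whether they were worsening.

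The cost is SAP wording, two tables and a request that drop-outs return their paper diaries. Diaries are collected at site visits and drop-outs get only a phone call, so some will be missing; with the SAP at V1.3 of April 2017, the request may come too late for earlier drop-outs. Patients lost to follow-up will not answer the call either. If half the diaries come back at random (5-entry minimum), A2.1 rejection falls only to 9–16% at OR 2 and 16–28% at OR 3. The fix reduces the possible bias without removing it.
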